#### 7.6.2 Secondary Analyses

The primary analysis of the treatment effect will be pooled over the two risk groups: MSM and heterosexual women. As a secondary analysis, separate Cox regressions will be used to estimate the relative risk and confidence interval for a treatment effect in the heterosexual women and MSM subgroups.

Adherence will be measured monthly. The analysis of adherence will be structured to allow us to estimate the adherence rate, test for a difference in compliance between the placebo and treatment groups, test for a trend over time in the compliance rate and examine the relationship between adherence and markers of risky sexual behavior. Specifically, a logistic regression with proportion of tablets taken each month as the outcome and treatment group, clustering of missed doses, time on study and markers of risky sexual behavior as predictors, will be used. Since the analysis will involve repeated observations on individuals, robust variance estimates , will be used to evaluate statistical significance and compute confidence intervals. Standard methods for model checking will be used to check the assumption of a linear trend over time in compliance.

The relationship between compliance and risk of incident HIV infection will also be examined. A proportional hazards model with HIV infection as the endpoint and self-reported adherence, subgroup (women versus MSM) and their interaction as covariates (time-dependent in the case of adherence) will be fit to the data from those individuals randomized to acyclovir. If the adherence is related to risky sexual behavior then the relationship between adherence and risk of HIV infection may be found to differ between MSM (where risk of HIV infection is also related to risky sexual behavior) and women (where risk of HIV infection is likely to be less related to the woman's sexual behavior and more related to her partner's behavior).

A proportional hazards model will be used to evaluate the effect of treatment arm on recurrence of genital ulcers. Since genital ulcers may recur multiple times over the course of follow-up, the model for recurrent events described by Anderson and Gill will be used for this analysis. Individuals will be considered to be not-at-risk for recurrences when they are being actively treated syndromically for herpes due to symptoms. The robust variance formulation described by Lin will be used to adjust the p-values and confidence intervals if multiple recurrences occur in one or more individuals. In addition, survival analysis will be performed with time to first recurrence as the dependent variable.

Through modeling, exploratory analyses will be conducted to assess the relative contribution of suppression of clinical versus subclinical

reactivation using acyclovir. To address this problem, a proportional hazards model will be fitted, with HIV seroincidence as the outcome and i) self-reported presence of genital ulcers within the past 1 month (yes/no, as well as a continuous variable), and ii) self-reported adherence to acyclovir (proportion of doses and days in which both doses were missed) as covariates. Actual use of acyclovir as opposed to randomization assignment will be used for this analysis. The (negative of the) coefficient for lesions in this model will provide a measure of the decrease in risk associated with suppression of clinical lesions. The coefficient for acyclovir will provide a measure of the protective effect of treatment after controlling for the presence of clinical lesions. Presumably, this additional protective effect is related to suppression of subclinical disease.

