## 2.3 Study Design

This is a phase III, multi-site, randomized, double-blind, placebo-controlled trial. Between 2820 and 3012 high-risk, HIV-negative, HSV-2 seropositive WSM and MSM will be enrolled. Women who have sex with men (WSM) will be enrolled at study sites in Lusaka, Zambia, Harare, Zimbabwe, and Johannesburg, South Africa. Men who have sex with men (MSM) will be enrolled at study sites in Lima, Iquitos, and Pucallpa, Peru; Seattle, WA, USA; New York City; NY, USA; and San Francisco, CA, USA.

Due to slow enrollment at the time of the printing of this version of the protocol, participant follow-up is increased from 12 months to 18 months. Newly enrolled participants will be followed for 18 months after enrollment. In addition, the Protocol Team will evaluate the benefit and feasibility of extending follow-up for currently enrolled participants at each site (extending from 12 to 18 months). Following this evaluation, the re-consent process will be further examined in the first month of implementation at each site involved in the process. The protocol team will then determine whether a particular site will continue re-consenting participants at that site. The sample size for the study will ultimately be determined by the proportion of currently enrolled participants who will be followed for 12 vs 18 months.

HSV-2 serostatus will be determined from samples taken at screening by Focus Technologies™ (formerly MRL) HSV-2 EIA. Participants with a low positive index between and including 0.9 and 3.4 according to the Focus serology, but are HSV-2 positive by the University of Washington's HSV-2 Western blot test, will also be eligble. HIV serostatus will be determined according to the algorithms presented in Appendices II and III. Confirmatory second samples will only be drawn in case of discordant test results on the first sample or if mandated by local law.

Pre-test, risk reduction, and post-test counseling will be provided to all participants; HSV-2 counseling will include information on the natural history of HSV-2, clinical

manifestations, recognition of prodromal symptoms and lesions, risk of transmission during subclinical reactivation as well as symptomatic herpetic lesions, and the epidemiologic and clinical data about HSV-2 and HIV interactions.

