#### 5.4 Follow-Up Visits: Monthly (Months 1 To 12 or 18)

The following activities will take place **each month**:

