The number of HIV negative individuals per arm (N) that must be followed to achieve a given number of events (L) depends on the duration of follow-up (f), the incidence rate in the baseline group (I), the relative risk (r) and the proportion lost to follow-up (ltf). The relationship between number of persons per arm and number of events is

$$N_{arm} \approx L/[I^*f^*(1+r)^*(1-ltf)]$$

We assume a 3.5% annual incidence rate over the first 12 months of enrollment and a 2.7% annual seroincidence rate in year 2 in WSM and MSM averaged across the participating US and non-US sites.We assume 8% lost to followup in the first year and 2% every 6 months thereafter. The relative risk is 0.51. The target followup is either 12 or 18 months as outlined in section 2.3 above. Newly enrolled participants will be followed for 18 months after enrollment. In addition, the Protocol Team will evaluate the benefit and feasibility of extending follow-up for currently enrolled participants at each site (extending from 12 to 18 months). Following this evaluation, the re-consent process will be further examined in the first month of implementation at each site involved in the process. The protocol team will then determine whether a particular site will continue re-consenting participants at that site, and whether participants who re-consented to additional follow-up will be followed for 12 or 18 months. The sample size for the study will ultimately be determined by the proportion of currently enrolled participants who will be followed for 12 vs 18 months.

Given similar incidence rates and enrollment numbers in the two risk groups (WSM and MSM), similar numbers of HIV seroconversions are expected in each group. With an expected number of 46.5 seroconversions and all other assumptions as above, the power to detect a relative risk of 0.51 in either risk group individually is 0.63 (without any adjustment for multiple testing), whereas the power to detect a relative risk of 0.427 is 0.80.

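### The adherence trend test in 7.6.2 may confound change over time with a change in who is measured after month 12

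*Supplement*

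**What the plan says.** Under 7.6.2, "Adherence will be measured monthly", and one stated purpose of the adherence analysis is to "test for a trend over time in the compliance rate". The model is "a logistic regression with proportion of tablets taken each month as the outcome and treatment group, clustering of missed doses, time on study"; the only other predictors it names are indicators of sexual risk-taking. Two safeguards are named: "Since the analysis will involve repeated observations on individuals, robust variance estimates", and "Standard methods for model checking will be used to check the assumption of a linear trend over time in compliance". The list of predictors has no site, risk group, enrolment period or planned length of follow-up.

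The heading of section 5.4 shows that the months observed vary by participant: "Follow-Up Visits: Monthly (Months 1 To 12 or 18". Section 2.3 explains why: "Newly enrolled participants will be followed for 18 months after enrollment", while those already enrolled stay at 12 months unless extended. Extension depends on a site-by-site evaluation and on the individual's re-consent, and section 7.3 adds: "The protocol team will then determine whether a particular site will continue re-consenting participants at that site". The share who will be followed for 18 months is not stated; the protocol says only that it will determine the final sample size.

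**The concern.** Months 1-12 are scheduled for everyone. Months 13-18 are scheduled only for a subset defined by enrolment date, site and willingness to take tablets for six more months. None of these is random, and each could plausibly go with adherence. A pooled model with a single time effect compares later months in the subset with earlier months in everybody. It cannot tell people changing from a change in the people measured.

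The named safeguards do not separate the two. Robust variance changes the standard error of the slope, not its estimate. A linearity check might show a step at month 12 but would not say what caused it.

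Assessing adherence is one of the two secondary objectives (2.2), and section 4.3 calls high adherence important for judging efficacy. If better adherers are over-represented late, the report could show rising adherence where there was none, or mask a real decline. If worse adherers are over-represented, the error runs the other way.

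**Working it through.** **1. Reproduce the protocol's event count.** Inputs from 7.3: r = 0.51, two-sided α = 0.05, power 90%.

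L = {(1.960 + 1.282) / (0.5 × ln 0.51)}² = 92.7, rounded up to 93, as stated.

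**2. Infer the share followed for 18 months.** Inputs from 7.3: incidence 3.5% per year in year 1 and 2.7% in year 2; loss of 8% in year 1 and a further 2% per six months (10% cumulative for months 13-18). With p the share followed for 18 months:

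93 = N × 1.51 × (0.035 × 0.92 + p × 0.027 × 0.5 × 0.90) = N × 1.51 × (0.0322 + p × 0.01215)

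- N = 1410 per arm: 93/(1.51 × 1410) = 0.04368; p = (0.04368 − 0.0322)/0.01215 = 0.94.
- N = 1506 per arm: 93/(1.51 × 1506) = 0.04090; p = (0.04090 − 0.0322)/0.01215 = 0.72.
- Bounds: everyone at 18 months gives N = 1389; everyone at 12 months gives N = 1913.

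So about 6% to 28% have no scheduled data after month 12. This rests on one reading of the loss term. Using 8% or 9% for months 13-18 moves the shares by only one or two points. Averaging the loss over each period (4% and 9%) gives 82% and 59%, which would make the missing share larger.

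**3. Effect on the slope.** Assume adherence is flat in every person, 90% in the 18-month cohort and lower by a fixed gap in the 12-month cohort, with no dropout. The 90% and the gaps are assumptions. The observed rate is the weighted mean of the cohorts in months 1-12 and the 18-month cohort alone afterwards. For 28% and a 10-point gap, that is 0.72 × 0.90 + 0.28 × 0.80 = 87.2%, then 90%. A logistic model with linear month and observations treated as independent gives:

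| Share in 12-month cohort | Gap (points) | Observed rate, months 1-12 → 13-18 | Spurious odds ratio, month 18 vs month 1 |
|---|---|---|---|
| 28% | 0 | no change | 1.00 |
| 28% | 2 | 89.4% → 90% | 1.07 |
| 28% | 5 | 88.6% → 90% | 1.18 |
| 28% | 10 | 87.2% → 90% | 1.37 |
| 6% | 10 | 89.4% → 90% | 1.08 |

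Adding a follow-up-cohort term returns an odds ratio of 1.00 in every row.

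**4. Would it be declared significant?** Simulation: 3012 people, 72% followed for 18 months, flat adherence, 85% in the 12-month cohort, person-clustered robust variance, independence fit, 200 runs per setting. The trend was significant at 5% in 3% of runs with no gap, 76% with a 2-point gap and 100% with a 5-point gap. With the cohort term, the rates at this 72% share were 6% to 6.5%. They depend on the assumed between-person and month-to-month variation.

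**5. Dependence on the working correlation.** For the 28%, 80%-versus-90% case, an exchangeable working correlation cut the odds ratio from about 1.37 to 1.01, 1.04 and 1.06 at within-person correlations of about 0.64, 0.43 and 0.29. In 12 runs per setting, the trend was still significant in about 8%, 42% and 75%.

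**The case against.** The strongest reply is that step 3 depends on a choice the protocol does not make. Section 7.6.2 cites reference 56 for the robust variance. In-text citations there run one ahead of the reference list: the recurrent-events model is cited as 57 but listed as 56, and the O'Brien-Fleming rule is cited as 59 but listed as 58. Citation 56 is therefore probably listed item 55, a paper on longitudinal data with discrete and continuous outcomes, which suggests a GEE-type analysis. With an exchangeable working correlation most of the artefact goes. This stands as a limit on size. It does not settle the point, because no working correlation is named and some false positives remain when within-person correlation is modest.

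Other points also stand in part. No separate analysis plan is shown, and covariate detail is often left to one; but 7.6.2 already lists its predictors, so this is a change to a stated model. Risk-behaviour covariates may absorb some of the cohort difference. At the 1410-per-arm end the effect is small. Months 1-12 are not a fixed population either: 8% loss is assumed in year 1, and women who become pregnant stop study drug.

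A reader might go further and infer that adherence is bound to appear to change, purely because the people measured change, and that a false significant trend is close to certain. The documents do not support that. They report no adherence difference between the cohorts; with no gap there is no artefact. The high rejection rates belong to an independence fit with assumed gaps.

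**Conclusion.** The point holds as a risk of confounding. The planned trend test mixes time on study with follow-up cohort, and nothing in the stated model separates them. Its size depends on three things the documents leave open: the adherence gap between cohorts, the share followed for 18 months (inferred here as 72% to 94%), and the working correlation. Under an independence-type fit and gaps of 2 to 10 points, the spurious odds ratio runs from about 1.07 to 1.37 at the 28% end, and is about 1.08 for a 10-point gap at the 6% end. The direction is unknown.

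The reach is narrow: one test within a secondary objective. Randomization is stratified by site, so the acyclovir-placebo comparison of adherence is largely unaffected. The primary Cox analysis of HIV infection is untouched. The change is worth making because it is cheap and is best fixed before unblinding.

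**What to change.** In 7.6.2, add to the adherence model site and an indicator of follow-up cohort with three levels: 12-month; re-consented to 18 months; enrolled for 18 months. As a sensitivity analysis, repeat the trend test over months 1-12 and, separately, within the 18-month cohorts. State the working correlation at the same time.

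The cost is a few sentences and no new data. The model gains a few parameters and the trend loses a little precision. Re-consent is decided after randomization, so the arm comparison should also be shown without the cohort indicator. Dropout and pregnancy-related stops of study drug will still change who is measured within months 1-12, so the restricted analysis reduces the problem without removing it.

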Monthly follow-up visits will be conducted to dispense study drug, collect bottles with any unused study drug from the prior month for a pill count, and provide adherence and condom counseling as well as condoms. A brief sexual history (number of partners, HIV serostatus of partners, if known), will be obtained. Female participants will be asked about their menstrual history since the last visit and, if indicated, be tested for pregnancy. These monthly assessments will enable more accurate assessment of adherence (both in terms of number of doses and clustering of missed doses which may have a greater impact on efficacy than total number of missed doses). In addition, the monthly clinical and behavioral assessments of herpes prodromal symptoms and other symptoms of genital herpes, and sexual activity will minimize recall bias, and thereby maximize the validity and reliability of the secondary outcome data.

Every 3 months, follow-up visits will be more extensive and include the following procedures in addition to the monthly assessments:

- A genital exam (examination of anal and genital regions) for signs of STD and genital ulcers.
- A more extensive sexual behavior questionnaire.
- HIV pre-test, risk reduction, and post-test counseling.
- Blood draw for HIV antibody testing.
- For female participants: a urine pregnancy test.

HIV incidence will be ascertained by HIV-1 EIA with Western blot (WB) or IFA confirmation according to one of the HIV algorithms provided in Appendices II and III. Thus, timing of HIV seroconversion will be ascertained within a three-month interval, which will enable more precise analyses of HIV seroconversion with respect to risk behavior, HSV-2 symptoms, and adherence with study drug. The presence of concurrent STDs, including syphilis and chancroid, will be assessed via questionnaire and supplemented by directed clinical exam, swab collection, NAAT testing, and other HSV-related genital findings, and by serologic testing for syphilis at enrollment and the end of study follow-up.

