# 4.3 Adherence Assessment

High adherence to acyclovir or placebo will be important for determining the efficacy of acyclovir in preventing HIV acquisition in this trial. The aim is to optimize and monitor adherence without excessive or unsustainable resource utilization that would make the results of this trial less generalizable in terms of implementation in developing countries.

At each monthly visit, study staff will assess participant compliance with the assigned treatment regimen through a structured interview and tablet count. Study product adherence and occurrence of genital lesions and other genital symptoms will be assessed via clinical interview and evaluation of the number of tablets

remaining in the bottles returned from their prior monthly supply of study drug. In addition, study staff will provide counseling about issues related to compliance with the study protocol, including counseling about what to do if a participant misses a dose.

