# 7.2.2 Secondary Endpoints

Consistent with the secondary study objectives, the following secondary endpoints will be assessed:

- Occurrence and frequency of genital ulcers
- Proportion of doses missed by study participants assigned to twice daily acyclovir and twice daily placebo.

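### The arm comparison of adherence is adjusted for clustering of missed doses, itself part of adherence, so it does not estimate the overall difference named as the endpoint and may mask or distort it

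*Supplement*

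**What the plan says.** Section 7.6.2 gives the adherence analysis four aims: estimate the adherence rate, "test for a difference in compliance between the placebo and treatment groups", test for a trend over time, and relate adherence to risk behaviour. It then specifies one model for them: "a logistic regression with proportion of tablets taken each month as the outcome and treatment group, clustering of missed doses, time on study", together with markers of risky sexual behaviour. Within-person correlation is handled as follows: "Since the analysis will involve repeated observations on individuals, robust variance estimates" are to be used.

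The endpoint being served, in section 7.2.2, is "Proportion of doses missed by study participants assigned to twice daily acyclovir and twice daily placebo". No covariate enters that definition.

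Section 2.3 says that the monthly visits allow adherence to be assessed more accurately, "both in terms of number of doses and clustering of missed doses which may have a greater impact on efficacy" than the total missed. Section 4.3 gives the data source: each month staff "assess participant compliance with the assigned treatment regimen through a structured interview and tablet count". Clustering is not defined for the adherence model. The nearest definition is in a different, exploratory model later in section 7.6.2, with HIV as the outcome, where adherence enters as "proportion of doses and days in which both doses were missed".

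**The concern.** Clustering describes how the missed doses of a month are arranged. A month without missed doses has no clustering, and every day on which both doses are missed lowers the proportion taken. The covariate and the outcome are thus two summaries of the same missed doses, and both arise after randomisation. Holding one fixed while comparing arms on the other answers a different question from the endpoint. The time coefficient is conditional in the same way.

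Adherence is one of two secondary objectives, and section 4.3 calls high adherence important for determining efficacy. Section 7.5 accepts that some placebo participants may suspect their assignment because lesions continue, so a difference in adherence between arms is conceivable. If it took the form of whole missed days, the pattern that section 2.3 suggests may matter more for efficacy, the specified model could hide it.

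**Working it through.** **Plan's own figure.** None exists. The documents give no effect size, power or arm-specific adherence rate for this analysis.

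**Algebra.** Assume a 30-day month at two doses a day, so 60 doses. Let B be the number of days with both doses missed and S the number of single misses. Then

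proportion taken = 1 - (2B + S)/60.

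If one arm has one more both-missed day per month and the same S, the overall difference is 2/60 = 3.3 percentage points. With B held fixed only S can vary, so on this linear scale the conditional arm difference is 0. If the arms differ only in S, holding B fixed leaves the difference in place. On the logit scale this holds only approximately.

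**Simulation (all settings assumed).**
- 400 people per arm, 12 months of 30 days, 200 runs per scenario.
- Both-missed days and single misses each have a daily or per-dose probability with logit -3.6 plus a person effect of SD 1. Reference adherence is then about 92%.
- The arm effect is a shift of 0.4 or 0.5 on one or both logits.
- Model: binomial-logit regression of proportion taken on arm and month, with variance clustered on person, without and then with a clustering covariate. Behaviour markers are not simulated.
- Clustering is coded three ways: the count B; the share 2B/(2B + S), set to 0 if nothing was missed; and any both-missed day (B > 0).

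Mean arm log odds ratio, with the share of runs with p < 0.05 in brackets:

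| What differs by arm | Adherence by arm | No clustering term | Count | Share | Any |
|---|---|---|---|---|---|
| Nothing | 92.04% / 92.01% | -0.004 (6.0%) | -0.001 (2.0%) | -0.003 (5.0%) | -0.002 (4.5%) |
| Both kinds of miss | 92.01% / 88.72% | -0.382 (100%) | -0.224 (99%) | -0.361 (100%) | -0.299 (100%) |
| Clustered misses only | 92.07% / 89.86% | -0.270 (100%) | -0.032 (10%) | -0.181 (92.5%) | -0.150 (85.5%) |
| Isolated misses only | 92.03% / 89.84% | -0.267 (99.5%) | -0.281 (100%) | -0.306 (100%) | -0.271 (100%) |
| More clustered, fewer isolated | 92.05% / 91.56% | -0.066 (20%) | +0.149 (93.5%) | +0.060 (18.5%) | +0.039 (13.5%) |

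**Relative change.**
- Clustered misses only: 1 - 0.032/0.270 = 88% lost with the count, 1 - 0.181/0.270 = 33% with the share, 1 - 0.150/0.270 = 44% with any.
- Both kinds: 1 - 0.224/0.382 = 41%, 1 - 0.361/0.382 = 5%, 1 - 0.299/0.382 = 22%.
- Isolated misses only: no loss. The coefficient moves slightly away from zero, by at most 0.306/0.267 - 1 = 15%.
- Opposite effects: the sign reverses under all three codings. With the count, 93.5% of runs are significant, on average in the direction opposite to the overall difference.

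**The case against.** The strongest reply is that the coefficient is a legitimate conditional comparison. With no arm difference it centres on zero and the test keeps its size (2.0% to 5.0%). When only isolated misses differ it barely moves. Even when only clustered misses differ, the share and any-day codings still reject in 92.5% and 85.5% of runs. All of this stands. A reader might infer that the planned comparison is simply wrong, or that most of a true difference would always vanish. The documents support neither: near-total masking needs the count coding together with a difference confined to clustered misses, and the protocol does not fix the coding. That detail is commonly left to an analysis plan, and none is among the documents, so the missing definition is not itself the fault. The choice of covariate is.

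A reader might also infer that a decline in adherence over time would largely be adjusted away. The same reasoning makes the time coefficient conditional, but the size of that effect was not calculated, so no such claim is made.

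Nor is it a fault in itself that behaviour markers appear in an adherence model, since relating adherence to behaviour is a stated aim. Finally, section 2.3 presents clustering as an aspect of adherence to be assessed, not as a named endpoint; section 7.2.2 lists only the proportion missed.

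Robust variance does not answer the point. It corrects the standard error and leaves unchanged what the coefficient estimates.

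**Conclusion.** The point holds as a mismatch between endpoint and model. Section 7.2.2 asks for the overall proportion of doses missed by arm, whereas the only model that section 7.6.2 specifies for the comparison yields the arm difference at a given level of clustering. The possible effect runs from almost none, through partial attenuation, to near-total masking or a reversed sign. Where it falls depends on a covariate not yet defined and on arm-specific patterns of missed doses that the documents do not give. The simulated figures illustrate that range under assumed rates and do not predict this trial's result. The harm is masking or distortion of a real difference, not false positives when the arms are alike.

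The reach is limited. The primary intention-to-treat Cox analysis, the 93 required seroconversions and the sample size do not use this model. The separate model of HIV on self-reported adherence among acyclovir recipients contains no clustering term, and the estimated adherence rate and the compliance reports to the DSMB remain available.

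**What to change.** In section 7.6.2, remove clustering of missed doses from the predictors of the model used for the arm and time-trend tests. Keep treatment, time on study and the randomisation stratum (site), with robust variance as planned.

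If clustering is of interest, define it, for example as the number of days with both doses missed, and describe it by arm as a separate adherence measure. Report the relation of adherence to risk-behaviour markers from an additional model labelled as associational.

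The cost is a change of wording before unblinding. It needs no data beyond the monthly interview, tablet count and behaviour questionnaires already planned.

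### The adherence–HIV model is fitted in the acyclovir arm only and without behaviour covariates, so its slope cannot separate a drug effect from the behaviour of people who adhere

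*Supplement*

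**What the plan says.** Section 7.6.2 plans a Cox-type analysis of HIV infection whose terms are "self-reported adherence, subgroup (women versus MSM) and their interaction as covariates (time-dependent in the case of adherence"). The analysis is confined to one arm: the model "will be fit to the data from those individuals randomized to acyclovir". No measure of sexual behaviour enters it, and no matching fit in the placebo arm is described. The plan then gives its reason for the subgroup term: "If the adherence is related to risky sexual behavior then the relationship between adherence and risk of HIV infection may be found to differ". The contrast it has in mind is women against MSM, because a woman's risk is thought to depend more on her partner's behaviour than on her own.

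The data for a comparison exist in both arms. Section 7.2.2 lists as a secondary endpoint "Proportion of doses missed by study participants assigned to twice daily acyclovir and twice daily placebo". Of the monthly visits, Section 4.3 says: "study staff will assess participant compliance with the assigned treatment regimen through a structured interview and tablet count". Section 5.4 has a risk behaviour and sexual history questionnaire at each monthly visit.

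Two neighbouring analyses bear on the point. A logistic regression in Section 7.6.2 does use both arms, with "treatment group, clustering of missed doses, time on study and markers of risky sexual behavior as predictors, will be used", but its outcome is tablets taken, not HIV. A later exploratory model, which does have HIV as outcome, states that "Actual use of acyclovir as opposed to randomization assignment will be used for this analysis".

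**The concern.** People who take their tablets reliably may differ from those who do not in condom use, number of partners or other determinants of HIV exposure. Within one arm, an association between adherence and HIV could come from the drug, from those differences, or from both, and the data of that arm alone cannot say which. In the placebo arm the blinded tablets are inert, so the association there largely reflects what kind of person adheres. That is the natural yardstick, and the planned model leaves it out.

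What is at stake is interpretation. Section 4.3 treats high adherence as important for determining efficacy, so this model is likely to be consulted if the intent-to-treat result is null or modest. The bias can run either way: if safer people adhere more, the slope flatters the drug; if people at higher risk adhere more, it can hide a real effect.

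**Working it through.** **Inputs from the protocol.** Two-sided alpha 0.05, relative risk 0.51, 93 events, 90% power; 46.5 events per risk group with power 0.63 (Section 7.3); 1:1 allocation (Schema). The strength of the adherence–behaviour link and the adherent share are not given, so those used below are assumptions. Adherence is simplified to a fixed yes/no variable.

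**The plan's own figures.** L = {(1.960 + 1.2816)/(0.5 × log 0.51)}² = 92.7, rounded up to 93. Power with 46.5 events at 0.51 is 0.63. Both reproduce. The plan gives no figure for the adherence model itself.

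**Events available.** At relative risk 0.51 the acyclovir arm has 93 × 0.51/1.51 = 31.4 events and the placebo arm 93/1.51 = 61.6. The planned model therefore sets aside about two thirds of the events. With an inert drug the split would be 46.5 and 46.5.

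**Size of the mixing with an inert drug (assumed link).** Half the cohort has three times the risk; 70% of them adhere against 90% of the rest.
- Adherent share: 0.5 × 0.7 + 0.5 × 0.9 = 0.80.
- High-risk share among adherent: 0.35/0.80 = 0.4375; among non-adherent: 0.15/0.20 = 0.75.
- Apparent relative risk: (1 + 2 × 0.4375)/(1 + 2 × 0.75) = 1.875/2.5 = 0.75.

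Reversing the link (90% in high-risk, 70% in the rest) gives shares 0.45/0.80 = 0.5625 and 0.05/0.20 = 0.25, and a relative risk of 2.125/1.5 = 1.42. With a drug effect of 0.51 among adherent people, the acyclovir-arm slope would be 0.51 × 0.75 = 0.38 in the first case and 0.51 × 1.42 = 0.72 in the second. Dividing the acyclovir-arm slope by the placebo-arm slope returns 0.51 in both, provided the link is the same in each arm.

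**Would it reach significance?** Taking 80% of events as adherent, the standard error of the log ratio with 46.5 events is √(1/(46.5 × 0.8 × 0.2)) = 0.37, and the chance of p < 0.05 at 0.75 is about 12% (about 10% with 31 events). With a stronger assumed behavioural hazard ratio of 0.6, 46.5 events per arm and 50–90% adherent, the chance is about 24–40%, against 5% for the two-arm interaction.

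**Simulation with an inert drug.** 300 trials of 1,500 per arm were run under another assumed link: 30% at 2.5-fold hazard, adherence 60% against 88%. There were about 71 events per arm, more than the plan expects. The mean acyclovir-only hazard ratio was 0.73, significant in 25% of trials; the median interaction was 1.01, significant in 6%.

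**Precision of the two candidate safeguards**, at 31.4 and 61.6 events with 80% of events adherent:
- Women against MSM within the acyclovir arm, about 15.7 events each: √(2/(15.7 × 0.16)) = 0.89, a 95% interval of about a factor 5.7 each way.
- Arm by adherence: √(1/(31.4 × 0.16) + 1/(61.6 × 0.16)) = 0.55, a factor of about 2.9 each way; power for 0.51 about 23%. Allowing the adherent share of events to differ by arm (behavioural hazard ratio 0.6, 50–90% adherent) gives 0.45–0.54, a factor of about 2.4–2.9, and power of about 24–33%.

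**The case against.** The plan does not ignore confounding. It names it, adds the subgroup interaction as a probe, and separately models adherence on behaviour. For this model it speaks only of examining a relationship, so a reader who infers that the slope is put forward as a causal effect goes beyond the text. The sentence that does take such a step, "The coefficient for acyclovir will provide a measure of the protective effect of treatment after controlling for the presence of clinical lesions", belongs to the other model, which is labelled exploratory. This stands as a limit on the charge. But the probe is no control: a difference between women and MSM could be a different drug effect, and similar slopes could be similar confounding, however precisely they are estimated.

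A reader might also infer that an inert drug is bound to show a benefit in adherers. The documents give no strength or direction for the link, and under the first illustration about nine trials in ten would show nothing significant.

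Nor is the placebo association pure behaviour. Placebo participants may be given open-label episodic acyclovir (Section 4.1), those who move to open-label suppressive therapy stay in their randomised group (Section 7.6.1), and those with continuing lesions may guess their arm (Section 7.5). The interaction is unbiased only if these do not make adherence track behaviour differently by arm. It is also imprecise. Both objections stand and have to be reported with it; neither makes the one-arm slope the better guide.

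Finally, self-report is not plainly the wrong measure. Monthly visits may be held by telephone (Section 5.4), drug may be delivered for up to three months without a visit (Section 4.1), a count needs returned bottles, and Section 2.3 suggests that clustering of missed doses may matter more than their total, which a count does not show. Requiring the tablet count as the main measure would be partly preference.

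**Conclusion.** The concern holds as a fault of a secondary analysis. As specified, the adherence slope in the acyclovir arm cannot be attributed to drug, behaviour or a mixture, and the planned subgroup interaction cannot settle it. The size is not knowable from the documents: the 0.75 (or 1.42 if the link is reversed) rests wholly on the assumed risk and adherence shares and on fixed yes/no adherence. The two-arm interaction removes this mixing if the adherence–behaviour link is alike in both arms, at the price of a 95% interval spanning a factor of about 2.4–2.9 each way and power of roughly 23–33% for a hazard ratio of 0.51. It should not be inferred that the trial's main conclusion is at risk: the intent-to-treat comparison, its sample size and its error rate are untouched.

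**What to change.** Reword this model in Section 7.6.2 as follows.
- Fit it in both arms, with arm, time-dependent adherence and arm-by-adherence interaction, stratified by risk group and adjusted for the behaviour measures already collected.
- Report the adherence association within each arm side by side. Base any statement about the drug on the interaction, as an estimate with its confidence interval and not as a test.
- State that this reading assumes a similar adherence–behaviour link in both arms. Read it with the planned between-arm comparison of adherence and a tabulation by arm of open-label acyclovir use.
- Repeat the model with tablet-count adherence as a sensitivity analysis.

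The cost is a change of wording and some additional analysis. No new data, visits or participants are needed. The price in interpretation is a wide interval, which should be stated in advance so that a null interaction is not read as proof of no drug effect.
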